5.5.1 Primary Efficacy Analysis

Analysis of the primary efficacy variable defined as PI based on evaluable cycles in non-breastfeeding women aged ≤ 35 years will be performed for the MFAS.

$$PI \text{ (evaluable cycles)} = \frac{\sum \text{on-drug pregnancy} \in \{\text{evaluable cycles}\}}{\#\{\text{evaluable cycles}\}} \times 1300.$$

Respective two-sided 95% CI for PI based on evaluable cycles will be calculated according to formula in Section 5.5.

Tables

No.	Name	Analysis set	Comments
Table 15.2.1.1.1	Pearl Index Based on Evaluable Cycles in Non-Breastfeeding Women Aged ≤ 35 Years (Only Confirmed Pregnancies, Excluding Sites 104 and 120)	Modified Full analysis	Number and percentage of confirmed on-drug pregnancies in the evaluable cycles will be presented. Number of evaluable cycles as well as PI and two-sided 95% CI will be presented. Table analysis will be based on MFAS. Data of centers 104 and 120 will be excluded.

5.5.2 Secondary Efficacy Analysis

Secondary Efficacy Analysis will be based on non-breastfeeding women. Also, analysis will be performed in BMI subgroups.

Overall PI

Overall PI will be calculated based on exposure cycles for all women, aged ≤ 35 years and aged > 35 years:

$$PI \text{ (exposure cycles)} = \frac{\sum \text{on-drug pregnancy} \in \{\text{exposure cycles}\}}{\#\{\text{exposure cycles}\}} \times 1300.$$

Respective two-sided 95% CI for overall PI will be calculated according to formula in Section 5.5.

PI for method failures

PI for method failures will be calculated based on perfect cycles for all women, aged ≤ 35 years and aged > 35 years. Number of pregnancies will be calculated according to method failure definition:

$$PI (method failure) = \frac{\sum \text{method failure pregnancy} \in \{\text{perfect cycles}\}}{\#\{\text{perfect cycles}\}} \times 1300.$$

Respective two-sided 95% CI for PI for method failures will be calculated according to formula in Section 5.5.

Evaluable cycles PI

Evaluable cycles PI will be calculated based on evaluable cycles for all women and women aged > 35 years:

$$PI (\text{evaluable cycles}) = \frac{\sum \text{on-drug pregnancy} \in \{\text{evaluable cycles}\}}{\#\{\text{evaluable cycles}\}} \times 1300.$$

Respective two-sided 95% CI for PI based on evaluable cycles will be calculated according to formula in Section 5.5.

Life table analysis for pregnancy rate

Method failure life table analysis and life table analysis on evaluable cycles will be performed in all women, women aged ≤ 35 and > 35 years in order to have the pregnancy rate at each cycle and cumulative pregnancy rates for 6 and 13 cycles.

Cumulative pregnancy rate will be calculated by using the **PROC LIFETEST** procedure:

```
PROC LIFETEST DATA=<data set> METHOD=KM OUTSURV=CL CONFTYPE=LOG;
      TIME <time variable>*<censorship flag>(1);
      RUN;
```

The Kaplan-Meier method will be used to estimate the cumulative pregnancy ratio. Logarithmic transformation will be used for 95% CI of the pregnancy rate. The period from the start of treatment until the pregnancy will be the time variable in this analysis. Subjects who did not become pregnant will be censored at their time of the last intake of IMP.

Tables

No.	Name	Analysis set	Comments
Table 15.2.1.2.1	Overall Pearl Index in Non-Breastfeeding Women (Only Confirmed Pregnancies, Excluding Sites 104 and 120)	Modified Full analysis	Number and percentage of confirmed on-drug pregnancies will be presented. Number of exposure cycles as well as PI and two-sided 95% CI will be presented. Table analysis will be based on MFAS. Data of centers 104 and 120 will be excluded.
Table 15.2.1.2.2	Overall Pearl Index in Non-Breastfeeding Women Aged ≤ 35 Years (Only Confirmed Pregnancies, Excluding Sites 104 and 120)	Modified Full analysis	Number and percentage of confirmed on-drug pregnancies will be presented. Number of exposure cycles as well as PI and two-sided 95% CI will be presented. Table analysis will be based on MFAS. Data of centers 104 and 120 will be excluded.
Table 15.2.1.2.3	Overall Pearl Index in Non-Breastfeeding Women Aged > 35 Years (Only Confirmed Pregnancies, Excluding Sites 104 and 120)	Modified Full analysis	Number and percentage of confirmed on-drug pregnancies will be presented. Number of exposure cycles as well as PI and two-sided 95% CI will be presented. Table analysis will be based on MFAS. Data of centers 104 and 120 will be excluded.
Table 15.2.1.2.4 _add	Overall Pearl Index in Non-Breastfeeding Women by BMI Subgroup (Only Confirmed Pregnancies, Excluding Sites 104 and 120)	Modified Full analysis	Number and percentage of confirmed on-drug pregnancies will be presented. Number of exposure cycles as well as PI and two-sided 95% CI will be presented by BMI subgroup. Table analysis will be based on MFAS. Data of centers 104 and 120 will be excluded.
Table 15.2.1.2.5 _add	Overall Pearl Index in Non-Breastfeeding Women by BMI Subgroup (Only Confirmed Pregnancies, Including Sites 104 and 120)	Modified Full analysis	Number and percentage of confirmed on-drug pregnancies will be presented. Number of exposure cycles as well as PI and two-sided 95% CI will be presented by BMI subgroup. Table analysis will be based on MFAS. Data of centers 104 and 120 will be included.

Table 15.2.1.2.6 _add	Overall Pearl Index in Non-Breastfeeding Women by BMI Subgroup (Confirmed and Suspected, Non-confirmed Pregnancies, Excluding Sites 104 and 120)	Modified Full analysis	Number and percentage of confirmed and suspected, non-confirmed on-drug pregnancies will be presented. Number of exposure cycles as well as PI and two-sided 95% CI will be presented by BMI subgroup. Table analysis will be based on MFAS. Data of centers 104 and 120 will be excluded.
Table 15.2.1.2.7 _add	Overall Pearl Index in Non-Breastfeeding Women by BMI Subgroup (Confirmed and Suspected, Non-confirmed Pregnancies, Including Sites 104 and 120)	Modified Full analysis	Number and percentage of confirmed and suspected, non-confirmed on-drug pregnancies will be presented. Number of exposure cycles as well as PI and two-sided 95% CI will be presented by BMI subgroup. Table analysis will be based on MFAS. Data of centers 104 and 120 will be included.
Table 15.2.1.2.8 _add	Overall Pearl Index in Non-Breastfeeding Women by Weight Subgroup (Only Confirmed Pregnancies, Excluding Sites 104 and 120)	Modified Full analysis	Number and percentage of confirmed on-drug pregnancies will be presented. Number of exposure cycles as well as PI and two-sided 95% CI will be presented by weight subgroup. Table analysis will be based on MFAS. Data of centers 104 and 120 will be excluded.
Table 15.2.1.2.9 _add	Overall Pearl Index in Non-Breastfeeding Women by Weight Subgroup (Only Confirmed Pregnancies, Including Sites 104 and 120)	Modified Full analysis	Number and percentage of confirmed on-drug pregnancies will be presented. Number of exposure cycles as well as PI and two-sided 95% CI will be presented by weight subgroup. Table analysis will be based on MFAS. Data of centers 104 and 120 will be included.
Table 15.2.1.2.10_add	Overall Pearl Index in Non-Breastfeeding Women by Weight Subgroup (Confirmed and Suspected, Non-confirmed Pregnancies, Excluding Sites 104 and 120)	Modified Full analysis	Number and percentage of confirmed and suspected, non-confirmed on-drug pregnancies will be presented. Number of exposure cycles as well as PI and two-sided 95% CI will be presented by weight subgroup. Table analysis will be based on MFAS. Data of centers 104 and 120 will be excluded.
Table 15.2.1.2.11_add	Overall Pearl Index in Non-Breastfeeding Women by Weight Subgroup (Confirmed and Suspected, Non-confirmed Pregnancies, Including Sites 104 and 120)	Modified Full analysis	Number and percentage of confirmed and suspected, non-confirmed on-drug pregnancies will be presented. Number of exposure cycles as well as PI and two-sided 95% CI will be presented by weight subgroup. Table analysis will be based on MFAS. Data of centers 104 and 120 will be included.
Table 15.2.1.3.1	Pearl Index for Method Failures in Non-Breastfeeding Women (Only Confirmed Pregnancies, Excluding Sites 104 and 120)	Modified Full analysis	Number and percentage of confirmed pregnancies in the perfect cycles will be presented. Number of perfect cycles as well as PI and two-sided 95% CI will be presented. Table analysis will be based on MFAS. Data of centers 104 and 120 will be excluded.
Table 15.2.1.3.2	Pearl Index for Method Failures in Non-Breastfeeding Women Aged \leq 35 Years (Only Confirmed Pregnancies, Excluding Sites 104 and 120)	Modified Full analysis	Number and percentage of confirmed pregnancies in the perfect cycles will be presented. Number of perfect cycles as well as PI and two-sided 95% CI will be presented. Table analysis will be based on MFAS. Data of centers 104 and 120 will be excluded.
Table 15.2.1.3.3	Pearl Index for Method Failures in Non-Breastfeeding Women Aged $>$ 35 Years (Only Confirmed Pregnancies, Excluding Sites 104 and 120)	Modified Full analysis	Number and percentage of confirmed pregnancies in the perfect cycles will be presented. Number of perfect cycles as well as PI and two-sided 95% CI will be presented. Table analysis will be based on MFAS. Data of centers 104 and 120 will be excluded.
Table 15.2.1.4.1	Pearl Index Based on Evaluable Cycles in Non-Breastfeeding Women (Only Confirmed Pregnancies, Excluding Sites 104 and 120)	Modified Full analysis	Number and percentage of confirmed pregnancies in the evaluable cycles will be presented. Number of evaluable cycles as well as PI and two-sided 95% CI will be presented. Table analysis will be based on MFAS. Data of centers 104 and 120 will be excluded.
Table 15.2.1.4.2	Pearl Index Based on Evaluable Cycles in Non-Breastfeeding Women Aged $>$ 35 Years (Only Confirmed Pregnancies, Excluding Sites 104 and 120)	Modified Full analysis	Number and percentage of confirmed pregnancies in the evaluable cycles will be presented. Number of evaluable cycles as well as PI and two-sided 95% CI will be presented. Table analysis will be based on MFAS. Data of centers 104 and 120 will be excluded.
Table 15.2.1.4.3 _add	Pearl Index Based on Evaluable Cycles in Non-Breastfeeding Women Aged \leq 35 Years (Only Confirmed Pregnancies, Including Sites 104 and 120)	Modified Full analysis	Number and percentage of confirmed on-drug pregnancies in the evaluable cycles will be presented. Number of evaluable cycles as well as PI and two-sided 95% CI will be presented. Table analysis will be based on MFAS. Data of centers 104 and 120 will be included.

Table 15.2.1.4.4 _add	Pearl Index Based on Evaluable Cycles in Non-Breastfeeding Women Aged ≤ 35 Years (Confirmed and Suspected, Non-confirmed Pregnancies, Excluding Sites 104 and 120)	Modified Full analysis	Number and percentage of confirmed and suspected, non-confirmed on-drug pregnancies in the evaluable cycles will be presented. Number of evaluable cycles as well as PI and two-sided 95% CI will be presented. Table analysis will be based on MFAS. Data of centers 104 and 120 will be excluded.
Table 15.2.1.4.5 _add	Pearl Index Based on Evaluable Cycles in Non-Breastfeeding Women Aged ≤ 35 Years (Confirmed and Suspected, Non-confirmed Pregnancies, Including Sites 104 and 120)	Modified Full analysis	Number and percentage of confirmed and suspected, non-confirmed on-drug pregnancies in the evaluable cycles will be presented. Number of evaluable cycles as well as PI and two-sided 95% CI will be presented. Table analysis will be based on MFAS. Data of centers 104 and 120 will be included.
Table 15.2.1.4.6 _add	Pearl Index Based on Evaluable Cycles in Non-Breastfeeding Women Aged ≤ 35 Years by BMI Subgroup (Only Confirmed Pregnancies, Excluding Sites 104 and 120)	Modified Full analysis	Number and percentage of confirmed on-drug pregnancies in the evaluable cycles will be presented. Number of evaluable cycles as well as PI and two-sided 95% CI will be presented by BMI subgroup. Table analysis will be based on MFAS. Data of centers 104 and 120 will be excluded.
Table 15.2.1.4.7 _add	Pearl Index Based on Evaluable Cycles in Non-Breastfeeding Women Aged ≤ 35 Years by BMI Subgroup (Only Confirmed Pregnancies, Including Sites 104 and 120)	Modified Full analysis	Number and percentage confirmed of on-drug pregnancies in the evaluable cycles will be presented. Number of evaluable cycles as well as PI and two-sided 95% CI will be presented by BMI subgroup. Table analysis will be based on MFAS. Data of centers 104 and 120 will be included.
Table 15.2.1.4.8 _add	Pearl Index Based on Evaluable Cycles in Non-Breastfeeding Women Aged ≤ 35 Years by BMI Subgroup (Confirmed and Suspected, Non-confirmed Pregnancies, Excluding Sites 104 and 120)	Modified Full analysis	Number and percentage of confirmed and suspected, non-confirmed on-drug pregnancies in the evaluable cycles will be presented. Number of evaluable cycles as well as PI and two-sided 95% CI will be presented by BMI subgroup. Table analysis will be based on MFAS. Data of centers 104 and 120 will be excluded.
Table 15.2.1.4.9 _add	Pearl Index Based on Evaluable Cycles in Non-Breastfeeding Women Aged ≤ 35 Years by BMI Subgroup (Confirmed and Suspected, Non-confirmed Pregnancies, Including Sites 104 and 120)	Modified Full analysis	Number and percentage of confirmed and suspected, non-confirmed on-drug pregnancies in the evaluable cycles will be presented. Number of evaluable cycles as well as PI and two-sided 95% CI will be presented by BMI subgroup. Table analysis will be based on MFAS. Data of centers 104 and 120 will be included.
Table 15.2.1.4.10 _add	Pearl Index Based on Evaluable Cycles in Non-Breastfeeding Women Aged ≤ 35 Years by Weight Subgroup (Only Confirmed Pregnancies, Excluding Sites 104 and 120)	Modified Full analysis	Number and percentage of confirmed on-drug pregnancies in the evaluable cycles will be presented. Number of evaluable cycles as well as PI and two-sided 95% CI will be presented by weight subgroup. Table analysis will be based on MFAS. Data of centers 104 and 120 will be excluded.
Table 15.2.1.4.11 _add	Pearl Index Based on Evaluable Cycles in Non-Breastfeeding Women Aged ≤ 35 Years by Weight Subgroup (Only Confirmed Pregnancies, Including Sites 104 and 120)	Modified Full analysis	Number and percentage confirmed of on-drug pregnancies in the evaluable cycles will be presented. Number of evaluable cycles as well as PI and two-sided 95% CI will be presented by weight subgroup. Table analysis will be based on MFAS. Data of centers 104 and 120 will be included.
Table 15.2.1.4.12 _add	Pearl Index Based on Evaluable Cycles in Non-Breastfeeding Women Aged ≤ 35 Years by Weight Subgroup (Confirmed and Suspected, Non-confirmed Pregnancies, Excluding Sites 104 and 120)	Modified Full analysis	Number and percentage of confirmed and suspected, non-confirmed on-drug pregnancies in the evaluable cycles will be presented. Number of evaluable cycles as well as PI and two-sided 95% CI will be presented by weight subgroup. Table analysis will be based on MFAS. Data of centers 104 and 120 will be excluded.
Table 15.2.1.4.13 _add	Pearl Index Based on Evaluable Cycles in Non-Breastfeeding Women Aged ≤ 35 Years by Weight	Modified Full analysis	Number and percentage of confirmed and suspected, non-confirmed on-drug pregnancies in the evaluable cycles will be presented. Number of evaluable cycles as well as PI and two-sided 95% CI will be presented by weight subgroup. Table analysis will be based on MFAS. Data of centers 104 and 120 will be excluded.

	Subgroup (Confirmed and Suspected, Non-confirmed Pregnancies, Including Sites 104 and 120)		Table analysis will be based on MFAS. Data of centers 104 and 120 will be included.
Table 15.2.2.1.1	Overall Pregnancy Rate Life Table in Non-Breastfeeding Women (Only Confirmed Pregnancies, Excluding Sites 104 and 120)	Modified Full analysis	Life table with the confirmed on-drug pregnancy rate at each cycle and cumulative pregnancy rates for 6 and 13 cycles will be presented. Table analysis will be based on MFAS. Data of centers 104 and 120 will be excluded.
Table 15.2.2.1.2	Overall Pregnancy Rate Life Table in Non-Breastfeeding Women Aged \leq 35 Years (Only Confirmed Pregnancies, Excluding Sites 104 and 120)	Modified Full analysis	Life table with the confirmed on-drug pregnancy rate at each cycle and cumulative pregnancy rates for 6 and 13 cycles will be presented. Table analysis will be based on MFAS. Data of centers 104 and 120 will be excluded.
Table 15.2.2.1.3	Overall Pregnancy Rate Life Table in Non-Breastfeeding Women Aged $>$ 35 Years (Only Confirmed Pregnancies, Excluding Sites 104 and 120)	Modified Full analysis	Life table with the confirmed on-drug pregnancy rate at each cycle and cumulative pregnancy rates for 6 and 13 cycles will be presented. Table analysis will be based on MFAS. Data of centers 104 and 120 will be excluded.
Table 15.2.2.2.1	Evaluatable Cycles Pregnancy Rate Life Table in Non-Breastfeeding Women (Only Confirmed Pregnancies, Excluding Sites 104 and 120)	Modified Full analysis	Life table with the evaluable cycle pregnancy rate at each cycle and cumulative pregnancy rates for 6 and 13 cycles will be presented. Table analysis will be based on MFAS and confirmed pregnancies. Data of centers 104 and 120 will be excluded.
Table 15.2.2.2.2	Evaluatable Cycles Pregnancy Rate Life Table in Non-Breastfeeding Women Aged \leq 35 Years (Only Confirmed Pregnancies, Excluding Sites 104 and 120)	Modified Full analysis	Life table with the evaluable cycle pregnancy rate at each cycle and cumulative pregnancy rates for 6 and 13 cycles will be presented. Table analysis will be based on MFAS and confirmed pregnancies. Data of centers 104 and 120 will be excluded.
Table 15.2.2.2.3	Evaluatable Cycles Pregnancy Rate Life Table in Non-Breastfeeding Women Aged $>$ 35 Years (Only Confirmed Pregnancies, Excluding Sites 104 and 120)	Modified Full analysis	Life table with the evaluable cycle pregnancy rate at each cycle and cumulative pregnancy rates for 6 and 13 cycles will be presented. Table analysis will be based on MFAS and confirmed pregnancies. Data of centers 104 and 120 will be excluded.
Table 15.2.2.3.1	Method Failure Life Table in Non-Breastfeeding Women (Only Confirmed Pregnancies, Excluding Sites 104 and 120)	Modified Full analysis	Life table with the perfect cycle pregnancy rate at each cycle and cumulative pregnancy rates for 6 and 13 cycles will be presented. Table analysis will be based on MFAS and confirmed pregnancies. Data of centers 104 and 120 will be excluded.
Table 15.2.2.3.2	Method Failure Life Table in Non-Breastfeeding Women Aged \leq 35 Years (Only Confirmed Pregnancies, Excluding Sites 104 and 120)	Modified Full analysis	Life table with the perfect cycle pregnancy rate at each cycle and cumulative pregnancy rates for 6 and 13 cycles will be presented. Table analysis will be based on MFAS and confirmed pregnancies. Data of centers 104 and 120 will be excluded.
Table 15.2.2.3.3	Method Failure Life Table in Non-Breastfeeding Women Aged $>$ 35 Years (Only Confirmed Pregnancies, Excluding Sites 104 and 120)	Modified Full analysis	Life table with the perfect cycle pregnancy rate at each cycle and cumulative pregnancy rates for 6 and 13 cycles will be presented. Table analysis will be based on MFAS and confirmed pregnancies. Data of centers 104 and 120 will be excluded.
Table 15.2.3.1.1 _add	Overall Pearl Index in Non-Breastfeeding Women (Confirmed and Suspected, Non-confirmed Pregnancies, Including Sites 104 and 120)	Modified Full analysis	Number and percentage of confirmed and suspected, non-confirmed on-drug pregnancies will be presented. Number of exposure cycles as well as PI and two-sided 95% CI will be presented. Table analysis will be based on MFAS. Data of centers 104 and 120 will be included.
Table 15.2.3.1.2 _add	Overall Pearl Index in Non-Breastfeeding Women (Only Confirmed Pregnancies, Including Sites 104 and 120)	Modified Full analysis	Number and percentage of confirmed on-drug pregnancies will be presented. Number of exposure cycles as well as PI and two-sided 95% CI will be presented. Table analysis will be based on MFAS. Data of centers 104 and 120 will be included.
Table 15.2.3.1.3 _add	Overall Pearl Index in Non-Breastfeeding Women (Confirmed and Suspected, Non-confirmed Pregnancies, Excluding Sites 104 and 120)	Modified Full analysis	Number and percentage of confirmed and suspected, non-confirmed on-drug pregnancies will be presented. Number of exposure cycles as well as PI and two-sided 95% CI will be presented. Table analysis will be based on MFAS. Data of centers 104 and 120 will be excluded.

Listings

No.	Name	Analysis set	Comments
Listing 16.2.2.1	Pregnancy Determination	Enrolled	All on study pregnancies will be listed.
Listing 16.2.2.2	Pregnancy Outcome	Enrolled	All on study pregnancies with the outcome results will be listed.
Listing 16.2.2.3	Subjects' Decision to Become Pregnant	Enrolled	Information about subjects' decision to become pregnant will be listed.

Figures

No.	Name	Analysis set	Comments
Figure 15.2.1.1_a dd	Overall Pearl Index in Non-Breastfeeding Women by BMI and Race (Black or African-American vs White) (Only Confirmed Pregnancies, Excluding Sites 104 and 120)	Modified Full Analysis	Diagram showing the PI and 95%CI of confirmed on-drug pregnancies will be presented by race and BMI subgroups. Data of centers 104 and 120 will be excluded.
Figure 15.2.1.2_a dd	Overall Pearl Index in Non-Breastfeeding Women by BMI and Race (Black or African-American vs White) (Only Confirmed Pregnancies, Including Sites 104 and 120)	Modified Full Analysis	Diagram showing the PI and 95%CI of confirmed on-drug pregnancies will be presented by race and BMI subgroups. Data of centers 104 and 120 will be included.
Figure 15.2.1.3_a dd	Overall Pearl Index in Non-Breastfeeding Women by BMI and Race (Black or African-American vs White) (Confirmed and Suspected, Non-confirmed Pregnancies, Excluding Sites 104 and 120)	Modified Full Analysis	Diagram showing the PI and 95%CI of confirmed and suspected, non-confirmed on-drug pregnancies will be presented by race and BMI subgroups. Data of centers 104 and 120 will be excluded.
Figure 15.2.1.4_a dd	Overall Pearl Index in Non-Breastfeeding Women by BMI and Race (Black or African-American vs White) (Confirmed and Suspected, Non-confirmed Pregnancies, Including Sites 104 and 120)	Modified Full Analysis	Diagram showing the PI and 95%CI of confirmed and suspected, non-confirmed on-drug pregnancies will be presented by race and BMI subgroups. Data of centers 104 and 120 will be included.
Figure 15.2.2.1_a dd	Overall Pearl Index in Non-Breastfeeding Women by BMI and Ethnicity (Only Confirmed Pregnancies, Excluding Sites 104 and 120)	Modified Full Analysis	Diagram showing the PI and 95%CI of confirmed on-drug pregnancies will be presented by ethnicity and BMI subgroups. Data of centers 104 and 120 will be excluded.
Figure 15.2.2.2_a dd	Overall Pearl Index in Non-Breastfeeding Women by BMI and Ethnicity (Only Confirmed Pregnancies, Including Sites 104 and 120)	Modified Full Analysis	Diagram showing the PI and 95%CI of confirmed and suspected, non-confirmed on-drug pregnancies will be presented by ethnicity and BMI subgroups. Data of centers 104 and 120 will be included.
Figure 15.2.2.3_a dd	Overall Pearl Index in Non-Breastfeeding Women by BMI and Ethnicity (Confirmed and Suspected, Non-Confirmed Pregnancies, Excluding Sites 104 and 120)	Modified Full Analysis	Diagram showing the PI and 95%CI of confirmed and suspected, non-confirmed on-drug pregnancies will be presented by ethnicity and BMI subgroups. Data of centers 104 and 120 will be included.
Figure 15.2.2.4_a dd	Overall Pearl Index in Non-Breastfeeding Women by BMI and Ethnicity (Confirmed and Suspected, Non-confirmed Pregnancies, Including Sites 104 and 120)	Modified Full Analysis	Diagram showing the PI and 95%CI of confirmed on-drug pregnancies will be presented by ethnicity and BMI subgroups. Data of centers 104 and 120 will be excluded.
Figure 15.2.3.1_a dd	Pearl Index Based on Evaluable Cycles in Non-Breastfeeding Women by BMI and Race (Black or African-American vs White) (Only Confirmed)	Modified Full Analysis	Diagram showing the PI and 95%CI of confirmed on-drug pregnancies will be presented by race and BMI subgroups. Data of centers 104 and 120 will be excluded.

	Pregnancies, Excluding Sites 104 and 120)	
--	--	--

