Duration of treatment for the individual subject: 13 sequential cycles of 28 days

Test product, dose and mode of administration:

LF111 coated tablets (4.0 mg drospirenone), oral administration

Reference therapy, dose and mode of administration: Not applicable.

Criteria for evaluation:

Efficacy:

Primary:

- Pearl index (PI) from evaluable cycles in non-breastfeeding women aged ≤ 35 years (at the time of trial enrollment)

Secondary:

- Pearl Index based on overall cycles (overall PI) in women aged ≤ 35 years (at the time of trial enrollment)
- PI for method failures in women aged ≤ 35 years (at the time of trial enrollment)
- Pregnancy ratio in women aged ≤ 35 years (at the time of trial enrollment)
- Overall PI, PI for method failures, PI (using evaluable cycles) and pregnancy ratio (life table analysis) in all women
- Overall PI, PI for method failures, PI (using evaluable cycles) and pregnancy ratio (life table analysis) in women aged > 35 years

Data from breastfeeding women will be excluded from the efficacy analyses but included in the analyses regarding safety and tolerability.

Safety/Tolerability:

- Adverse events (AEs)

- Vital signs
- Clinical laboratory parameters
- Vaginal bleeding pattern
- IMP acceptability

Pharmacokinetics:

- DRSP plasma concentrations
- Area under the curve (AUC)
- Volume of distribution
- Apparent clearance

Statistical methods:**Statistical analysis:**

Analysis of the primary efficacy variable defined as PI based on evaluable cycles in non-breastfeeding women aged ≤ 35 years (at the time of trial enrollment) will be performed for the Full Analysis Set (FAS). Two-sided 95% confidence interval (CI) for the PI will be calculated assuming that events of pregnancy have a Poisson distribution.

Secondary efficacy analysis will be based on the FAS. Two-sided 95% CIs will be calculated for the overall PI and the method failures PI.

Life table analysis: The pregnancy rate at each cycle and the cumulative pregnancy rate will be calculated (95% CI).

Analysis of safety endpoints will be conducted using the Safety Set only.

All adverse events (AEs) and treatment-emergent AEs (TEAEs) will be summarized by calculating the number and percent of subjects with AEs by preferred term and system organ class. Also TEAEs will be summarized by severity and relationship to treatment. Number and percent of TEAEs leading to trial termination will be provided.

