2.6 Sample Size

At least 920 subjects will be allocated to treatment to have at least 5000 evaluable cycles for the PI calculation in non-breastfeeding women aged ≤ 35 years (at the time of trial enrollment). Additionally, a minimum of 75 subjects aged > 35 years will be allocated to treatment. The calculations are based on empirical values including firstly a rate of 24.8% of subjects using back-up contraception or not having intercourse. Secondly, 45% of subjects are assumed to drop out of the trial. The prime target is to collect at least 5000 evaluable cycles.

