5.5 Efficacy Analysis

Primary and secondary efficacy analysis will be based on calculations of the PI in several different cases for non-breastfeeding women. The general formula of PI is

$$PI(<\text{set of cycles}>) = \frac{\sum \text{on-drug pregnancy} \in \{<\text{set of cycles}>\}}{\#\{<\text{set of cycles}>\}} \times 1300.$$

A two-sided 95% CI for the PI will be calculated assuming that events of pregnancy have a Poisson distribution. The CI will be calculated using the following equations from Gerlinger et al. [4]:

$$CI_{lower}(PI(<\text{set of cycles}>)) = \frac{1300}{\#\{<\text{set of cycles}>\}} \times CI_{lower}(\#\{\text{pregnancy} \in \{<\text{set of cycles}>\}\}),$$

$$CI_{upper}(PI(< set of cycles >)) \\ = \frac{1300}{\#\{< set of cycles >\}} \times CI_{upper}(\#\{pregnancy \in \{< set of cycles >\}\}),$$

where

$$CI_{lower}(\#\{pregnancy \in \{< set of cycles >\}\}) \\ = 0.5\chi^2(0.025; 2 \times \#\{pregnancy \in \{< set of cycles >\}\}),$$

$$CI_{upper}(\#\{pregnancy \in \{< set of cycles >\}\}) \\ = 0.5\chi^2(0.025; 2 \times \#\{pregnancy \in \{< set of cycles >\}\} + 1),$$

where $\chi^2(\alpha; n) = \alpha$ -Quantile of χ^2 -distribution with parameter n .

The following information from Pregnancy Notification forms will be taken:

- Subject ID number
- Estimated date of conception
- Method(s) Used to Estimate Conception Date

Efficacy analysis definitions

Term	Definition
Confirmed pregnancy	Subject reported a positive urine home pregnancy test and the pregnancy was confirmed by qualitative urine pregnancy test (β -hCG) and quantitative serum pregnancy test (β -hCG).
Suspected, non-confirmed pregnancy	Subject reported a positive urine home pregnancy test but confirmatory qualitative urine pregnancy test (β -hCG) and/or quantitative serum pregnancy test (β -hCG) are missing.
Suspected, subject confirmed not pregnant	Subject reported a positive urine home pregnancy test but confirmatory qualitative urine pregnancy test (β -hCG) and/or quantitative serum pregnancy test (β -hCG) are negative.
On-drug pregnancy	An on-drug pregnancy includes all conceptions that occur from Day 1 (the initiation of study medication) through seven days after the final tablet (active or placebo) is taken.

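### Life-table intervals coded with CONFTYPE=LOG set the upper pregnancy-rate limit too low when pregnancies are few, and the SAP sentence leaves open what is logged

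*SAP*

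**What the plan says.** SAP 5.5.2 (life table analysis) sets the estimator: "The Kaplan-Meier method will be used to estimate the cumulative pregnancy ratio". The PROC LIFETEST call carries the options "METHOD=KM OUTSURV=CL CONFTYPE=LOG", and the text adds: "Logarithmic transformation will be used for 95% CI of the pregnancy rate". Results are to be given for each cycle and as "cumulative pregnancy rates for 6 and 13 cycles". They fill nine tables (15.2.2.1.1 to 15.2.2.3.3): overall, evaluable-cycle and method-failure, each for all women, women aged 35 or under and women over 35.

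The protocol synopsis asks for a 95% interval on the life-table rates and names no transformation. The PI has its own interval in SAP 5.5: "A two-sided 95% CI for the PI will be calculated assuming that events of pregnancy have a Poisson distribution". SAP 2.6 sizes the trial on cycles: "At least 920 subjects will be allocated to treatment to have at least 5000 evaluable cycles for the PI calculation", and "a minimum of 75 subjects aged > 35 years will be allocated to treatment". Neither document states an expected PI or pregnancy count, or a rule for a life table without pregnancies.

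**The concern.** CONFTYPE=LOG builds the interval on log S, where S is the probability of no pregnancy. When S is close to 1, log S is almost linear in S. The transformation then does little, and the limits sit nearly symmetrically around the estimate. The sampling distribution of a small count is skewed to the right, so a symmetric interval stops too soon at the top and reaches too far at the bottom. For a contraceptive the upper limit is the one read as the worst plausible failure rate, so the error runs in the product's favour.

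The wording adds an ambiguity. A programmer following the code logs S. A reader could take the sentence to mean that the pregnancy rate 1 - S is logged, which gives different limits.

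**Working it through.** **Inputs.** From SAP 2.6: 920 women aged 35 or under, at least 75 women over 35, 45% dropout, 24.8% non-evaluable, target 5000 evaluable cycles. From SAP 5.5.2: Kaplan-Meier, 95%, 13 cycles. Assumed, because the documents give none: a true PI of 1 to 4, constant risk, and dropout at a constant rate over the 13 cycles.

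**The plan's own figure.** 920 × 13 × 0.55 × 0.752 = 4947 evaluable cycles. Conversely, 5000 / (13 × 0.55 × 0.752) = 929.9, so about 930 women against 920 stated (1.1% apart). The planning inputs are read correctly. The simulations below let women who leave contribute cycles until they go, which gives about 6900 evaluable cycles. The contrast between the options depends almost wholly on the number of pregnancies, d.

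**Formulas.** Let G be the Greenwood sum and H = -ln S.
- LOG upper limit: 1 - S·exp(-1.96√G), which is H + 1.96√G on the hazard scale.
- LOGLOG upper limit: 1 - S^exp(1.96√G/H), which is H·exp(1.96√G/H).

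For rare events √G/H ≈ 1/√d. The limits, as multiples of H, are therefore about 1 ± 1.96/√d for LOG and exp(±1.96/√d) for LOGLOG. The exact Poisson limits are χ²(0.025; 2d)/(2d) and χ²(0.975; 2d+2)/(2d).

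| d | LOG | LOGLOG | Exact | LOG upper / exact upper |
|---|---|---|---|---|
| 1 | 0 to 2.960 | 0.141 to 7.099 | 0.025 to 5.572 | 0.53 |
| 2 | 0 to 2.386 | 0.250 to 3.998 | 0.121 to 3.612 | 0.66 |
| 3 | 0 to 2.132 | 0.323 to 3.101 | 0.206 to 2.922 | 0.73 |
| 5 | 0.123 to 1.877 | 0.416 to 2.403 | 0.325 to 2.334 | 0.80 |
| 10 | 0.380 to 1.620 | 0.538 to 1.859 | 0.480 to 1.839 | 0.88 |
| 15 | 0.494 to 1.506 | 0.603 to 1.659 | 0.560 to 1.649 | 0.91 |
| 20 | 0.562 to 1.438 | 0.645 to 1.550 | 0.611 to 1.544 | 0.93 |

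The LOG lower limit is cut at 0 whenever 1.96/√d exceeds 1, that is for d of 3 or fewer.

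**As 13-cycle rates with 920 women** (LOG / LOGLOG / exact):
- 3 pregnancies: 0.00-1.20% / 0.18-1.76% / 0.12-1.63%
- 10 pregnancies: 0.69-3.01% / 1.00-3.46% / 0.90-3.40%
- 20 pregnancies: 2.07-5.29% / 2.38-5.70% / 2.27-5.64%

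Logging the pregnancy rate itself gives an upper limit of 3.47% at 10 pregnancies. The two readings of the sentence therefore differ by almost half a percentage point (3.01% against 3.47%).

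**Share of simulated trials with the true rate above the upper limit** (nominal 2.5%, 920 women):

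| Assumed PI | LOG, all cycles at risk | LOGLOG, all cycles at risk | LOG, 75.2% of cycles evaluable | LOGLOG, 75.2% of cycles evaluable |
|---|---|---|---|---|
| 1 | 8.0% | 0.7% | 9.3% | 0.6% |
| 2 | 6.1% | 1.8% | 6.4% | 1.3% |
| 4 | 4.7% | 1.9% | 5.0% | 1.7% |

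The all-cycles columns skip trials with no pregnancy. The evaluable-cycle columns count them as misses. Two-sided coverage in the evaluable-cycle setting goes from 90.3%, 92.8% and 94.0% under LOG to 96.2%, 95.5% and 95.4% under LOGLOG.

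**The other limit.** With 920 women and all cycles at risk, the LOGLOG lower limit lies above the truth in about 2.8% to 3.4% of trials, against 0.7% to 1.2% for LOG.

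**75 women.** Given at least one pregnancy, all cycles at risk and PI 1 to 4, the LOG upper limit misses in only 0.0% to 2.9% of trials, and the LOGLOG lower limit misses in about 4% to 8%. If only evaluable cycles count, the lower-limit figure at PI 1 rises to about 17% (0.0592/0.3509), because it jumps with each added pregnancy. A table with no pregnancies occurs in 56% of trials at PI 1 and 32% at PI 2 with all cycles at risk. With evaluable cycles only, it occurs in 65% at PI 1 and 27% at PI 3.

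**The case against.** The best case for leaving the plan alone has four parts.

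- **LOG is a recognised option fixed in advance, and the protocol prescribes no other.** True, but the upper-limit shortfall at low counts remains.
- **The sentence does not contradict the code outright.** It does not say which quantity is logged and can be read consistently with logging S. That stands: it is an ambiguity to be cleared up.
- **The life tables are secondary and no threshold hangs on their limits.** That also stands. Women over 35 and method failures have PI intervals as well, so the life table is not their only upper limit.
- **LOGLOG has its own errors.** It moves some error to the lower limit, widens the interval, and overshoots the exact upper limit by 27% at 1 event and 11% at 2. This stands too, so a reader should not infer that the change is free. The widening is mostly what an adequate interval costs: at 3 events the LOGLOG width is 2.778 against 2.716 exact and 2.132 for LOG.

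A reader might also infer that the low upper limit is worst in the over-35 tables, since counts are smallest there. The figures for 75 women do not support that. Given a pregnancy, the upper limit rarely misses at PI 1 to 4. What shows in those tables is a lower limit cut at 0, which is conservative, and tables with no pregnancies at all, where neither option gives a usable interval. Counting those as misses, LOGLOG even covers less than LOG at PI 3 (68.7% against 72.9%, evaluable cycles only). For method failures the documents give no count from which to judge.

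**Conclusion.** The point holds as a modest improvement to secondary, descriptive tables. At an assumed PI of 1 to 4 in 920 women, the coded upper limit misses the true 13-cycle rate about two to three times as often as its nominal 2.5%, and the lower limit is cut at 0 with 1 to 3 pregnancies. The gap to the exact upper limit is 27% of that limit at 3 events and 12% at 10, and falls below 10% by 15.

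The size rests on assumed PIs, constant risk and constant dropout; the direction does not. The primary PI is calculated separately and is unaffected, so nothing here supports doubt about the primary analysis.

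**What to change.** Use CONFTYPE=LOGLOG for all nine life tables. Replace the sentence with one stating that the 95% interval uses the complementary log-log transformation of the survival estimate, with limits for the pregnancy rate taken as one minus those for S.

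Add a rule that a life table with no pregnancies reports an exact Poisson or binomial upper limit. As an illustration, zero events give an upper Poisson count of -ln(0.025) = 3.689. With 565 evaluable cycles, the simulated exposure for 75 women, the 13-cycle upper limit would be 1 - exp(-3.689 × 13/565) = 8.1%.

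The cost is one code option, one sentence and one rule, with no extra subjects or data. In return, intervals are wider on the cumulative-hazard scale (30% at 3 events, 13% at 5, 6% at 10, 3% at 20). The lower limit is slightly anti-conservative with 920 women and more so with 75, and the upper limit is conservative with 1 or 2 pregnancies. For a failure rate, that last error is the safer one.
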